8. SELECTION OF SUBJECTS

8.1. Subject Inclusion Criteria

The subjects who fulfill the following criteria will be included in the study:

- 1. Subject provides written informed consent and is willing and able to comply with the protocol in the opinion of the Investigator.
- 2. Subject has completed 6 weeks of double-blind treatment and all scheduled assessments from Visit 6/EOT (Day 42) of the lead-in study of SEP-4199 CR.
- 3. Subject is medically appropriate for long-term open-label treatment with SEP-4199 CR in the opinion of the Investigator.
- 4. Female subjects of childbearing potential must agree to use effective and reliable contraception throughout the study and for at least 30 days after the last dose of study drug has been taken. In the Investigator's judgment, the subject will adhere to this requirement. Contraception requirements are detailed in Section 10.4.
- 5. Male subjects agree to avoid fathering a child and to use effective methods of birth control throughout the study and until at least 90 days after the last study drug administration. Contraception requirements are detailed in Section 10.4.

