15.4.3.2. Treatment-Emergent Mania

Treatment-emergent mania is defined as a YMRS score of ≥ 16 on any 2 consecutive OL visits (ie, including OL Baseline visit for subjects previously randomized to SEP380-4199 CR group or excluding the visit(s) with study day \leq Day 1 for subjects previously randomized to placebo group) or at the final assessment in the OL treatment period, or any treatment-emergent AE of mania or hypomania. If a subject has reported no AE of mania or hypomania and has no YMRS assessment (including OL Baseline for subjects previously randomized to SEP380-4199 CR group or has no post-OL Baseline YMRS assessment for subjects previously randomized to placebo), incidence of treatment-emergent mania will be set to missing.

For YMRS total score, descriptive statistics will be provided for observed values and changes from DB Baseline and OL Baseline, respectively, by study visit and analysis group.

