### 6.1. SAFETY POPULATION

The Safety Population will consist of all subjects who are enrolled and have received at least one dose of study drug during the 52-week open-label extension treatment period. The Safety Population will be used for the long-term safety, tolerability, and efficacy analyses. Subjects will be analyzed according to the following 3 treatment groups:

- PBO-SEP: Subjects whose actual treatment group is Placebo in study SEP380-301 and received SEP-4199 CR in study SEP380-303.
- SEP-SEP: Subjects whose actual treatment group is either SEP-4199 CR 200 mg/day or SEP-4199 CR 400 mg/day in study SEP380-301 and received SEP-4199 CR in study SEP380-303.
- ALL EXT: all subjects received SEP-4199 CR in study SEP380-303.

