### 18.1. ADVERSE EVENTS

Adverse Events (AEs) and pre-treatment events will be coded using MedDRA central coding dictionary, Version 22.0.

The concept of “pre-treatment events” only applies to study SEP380-301. Pre-treatment events are untoward medical occurrences that started prior to the first dose of study medication in SEP380-301.

Adverse events of study SEP380-301 are untoward medical occurrences that started at the same time of or after the first dose of study medication in SEP380-301, but before the first dose of OLE study medication in SEP380-303. These events will be recorded in the SEP380-301 databases.

Adverse events (AEs) of the SEP380-303 extension study are untoward medical occurrences that started at the same time of or after the first dose of the OLE study drug. These events will be recorded in the SEP380-303 database.

AEs (and pre-treatment events) that started in study SEP380-301 and are ongoing at the time of subject rollover will be re-entered into the SEP380-303 database and continue to be followed. These events will not be included in any AE summary table of SEP380-303. They will only be listed in a separate data listing.

Whenever available, the time information should be accounted for to determine if a record in the SEP380-303 AE database belongs to study SEP380-301 or SEP380-303. In the case where time is not available, untoward medical occurrences that started prior to the day of the first OLE dose will be considered to belong to study SEP380-301; those that started after the day of the first OLE dose will be considered to belong to study SEP380-303. Events that started on the same day of the first OLE dose will be assigned to study SEP380-301 or SEP380-303 depending on whether this AE record also exists in the SEP380-301 database (based on a comparison of subject ID, verbatim term, AE start date (and time if available), severity, and seriousness).

See [APPENDIX 2](#) for handling of partial dates for AEs.

Overall summary of the incidence of all AEs, study medication-related AEs, severe AEs, serious AEs, AEs leading to discontinuation from study, AEs leading to death, and AEs of special interest (AESI) will be provided by the actual treatment groups.

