### 18.3.1. ECG POTENTIALLY CLINICALLY SIGNIFICANT CRITERIA

QTc interval prolongation in adult subjects will be identified in accordance with the following predefined Potentially clinically significant criteria (same criteria apply to both QTcF and QTcB):

- > 450 msec for males \ > 470 msec for females at any post-OL Baseline time point (including unscheduled visits) not present at DB Baseline
- > 450 msec for males \ > 470 msec for females at any post-OL Baseline time point (including unscheduled visits) not present at OL Baseline
- > 480 msec at any post-OL Baseline time point (including unscheduled visits) not present at DB Baseline
- > 480 msec at any post-OL Baseline time point (including unscheduled visits) not present at OL Baseline
- > 500 msec at any post-OL Baseline time point (including unscheduled visits) not present at DB Baseline
- > 500 msec at any post-OL Baseline time point (including unscheduled visits) not present at OL Baseline
- $\geq 30$  msec increase from DB Baseline for at least one post-OL Baseline measurement (including unscheduled visits) and < 60 msec increase from DB Baseline for all post-OL Baseline measurements (including unscheduled visits)
- $\geq 30$  msec increase from OL Baseline for at least one post-OL Baseline measurement (including unscheduled visits) and < 60 msec increase from OL Baseline for all post-OL Baseline measurements (including unscheduled visits)
- $\geq 60$  msec increase from DB Baseline for at least one post-OL Baseline measurement (including unscheduled visits)
- $\geq 60$  msec increase from OL Baseline for at least one post-OL Baseline measurement (including unscheduled visits)

Except for the potentially clinically significant QTc criteria as described above, the PCS ECG measurements will be identified in accordance with the following predefined PCS criteria:

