### **18.6.2. YOUNG MANIA RATING SCALE (YMRS)**

The YMRS will be administered as a safety assessment and to inform the identification of treatment-emergent mania or hypomania.

The YMRS is a clinician-rated 11-item instrument used to assess the severity of mania in subjects with a diagnosis of bipolar disorder. The 11 items assess: Elevated Mood, Increased Motor Activity/Energy, Sexual Interest, Sleep, Irritability, Speech (Rate and Amount), Language/Thought Disorder, Content, Disruptive-Aggressive Behavior, Appearance, and Insight. The YMRS total score is the sum of the 11 individual items and ranges from 0 to 60. A higher score is associated with a greater severity of mania.

If one or more items are missing at a visit, the total score will be set to missing.

YMRS is assessed at Week 2 and monthly and at these study visits: from Visit 1E (coinciding with Visit 6 of SEP380-301) to Visit 15E.

Treatment-emergent mania or hypomania is defined as a YMRS total score  $\geq 16$  at any 2 consecutive post-OL Baseline visits or at the final visit, or an AE of mania or hypomania during the post-OL Baseline extension period (including both the OLE treatment period and the OLE follow-up period up to and including 7 days post the last OLE dose).

The DB Baseline and OL Baseline YMRS total score will be derived as described in [Section 7.2](#). The change from DB Baseline and OL Baseline in YMRS total score will be derived as described in [Section 7.7](#).

The observed values of YMRS total score at both the DB Baseline and the OL Baseline, and at each scheduled OLE study visit (starting from Visit 2E) and LOCF, will be summarized descriptively.

Changes from DB Baseline in YMRS total score will be summarized for each scheduled OLE study visit (starting from Visit 1E) and LOCF. Changes from OL Baseline will be summarized for each scheduled post-OL Baseline extension study visit (starting from Visit 2E) and LOCF.

Frequency and percentage of subjects experiencing treatment-emergent mania at any time during the study will be presented by treatment group.

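### For former placebo subjects, the YMRS part of treatment-emergent mania has no condition on the OL Baseline score, so an episode carried in from placebo can be counted as emerging on SEP-4199 CR

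*SAP*

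**What the plan says.** SAP 18.6.2 defines treatment-emergent mania or hypomania as a YMRS total of 16 or more "at any 2 consecutive post-OL Baseline visits or at the final visit, or an AE of mania or hypomania", within the post-OL Baseline extension period up to 7 days after the last dose. Reporting is a simple count: "Frequency and percentage of subjects experiencing treatment-emergent mania at any time during the study will be presented by treatment group". The scale is rated "from Visit 1E (coinciding with Visit 6 of SEP380-301) to Visit 15E", so an OL Baseline score is collected.

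Three other places define the same endpoint, and none conditions on the baseline score:

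- Protocol 6.1 and SAP 3.2.2 ask for one post-Baseline score of 16 or more.
- Protocol 11.4.6.2 asks for two consecutive post-Baseline visits or the final visit.
- Protocol 15.4.3.2 asks for two consecutive OL visits or the last assessment of the OL treatment period. It includes the OL Baseline visit for subjects previously on SEP-4199 CR and, for former placebo subjects, counts "excluding the visit(s) with study day" up to Day 1 left out.

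For adverse events, SAP 18.1 assigns anything that began before the first extension dose to the lead-in study. Of events still ongoing at rollover it says: "These events will not be included in any AE summary table of SEP380-303".

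PBO-SEP is defined in SAP 6.1 as: "Subjects whose actual treatment group is Placebo in study SEP380-301 and received SEP-4199 CR in study SEP380-303". None of the nine exclusion criteria in Protocol 8.2 names YMRS or mania. The relevant screen is the general one in Protocol 8.1: "Subject is medically appropriate for long-term open-label treatment with SEP-4199 CR in the opinion of the Investigator".

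**The concern.** In PBO-SEP, anything present at OL Baseline arose before the first dose of SEP-4199 CR. If a manic episode that began on placebo persists into the extension, the YMRS part of the definition can label it treatment-emergent, while the AE part of the same composite excludes it. One episode then gets opposite answers from the two halves of one endpoint.

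Switch to mania is a listed safety endpoint and a natural question for a drug given in bipolar depression. PBO-SEP is the group in which new onset on drug can be read over the whole exposure. The analysis is descriptive, so the reported percentage is itself the result. Observed YMRS values and changes are summarised by visit, but no planned summary table separates carried-over cases from new ones.

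**Working it through.** The documents give no incidence to reproduce. The check applies the written rules to illustrative YMRS sequences for a former placebo subject, then works out what one case is worth.

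**Inputs.** Threshold 16 (SAP 18.6.2). Rules from SAP 18.6.2, Protocol 15.4.3.2 (former placebo version) and SAP 3.2.2. Enrolled: 64 (SAP 4.4). The PBO-SEP size is not given; 16, 21 and 32 are assumed (one quarter, one third and one half of 64).

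**Step 1: who is counted.** The first number is OL Baseline, the rest are later visits, and the last is the final visit. The score sequences are invented to exercise the rules.

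| Sequence | SAP 18.6.2 | Protocol 15.4.3.2 | SAP 3.2.2 | PBO-SEP rule under fix |
|---|---|---|---|---|
| 20, then 18, 17, 8, 6, 5 | counted | counted | counted | separate line |
| 20, then 19 (early termination) | counted | counted | counted | separate line |
| 20, then 18, 10, 8, 6, 5 | no | no | counted | no |
| 20, then 10, 8, 6, 5, 5 | no | no | no | no |
| 6, then 8, 18, 20, 12, 9 | counted | counted | counted | counted |
| 17, then 5, later 25, 28 | counted | counted | counted | counted |

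The first two rows are the problem: nothing began on drug, yet the subject is counted. Rows three and four show that a high OL Baseline score alone is not enough under SAP 18.6.2. Row five is a true new onset and is unaffected. Row six is a new episode after the score fell below 16.

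**Step 2: the AE part on the same episode.** If the first-row episode had been recorded as an AE with onset in the lead-in, SAP 18.1 would keep it out of the extension AE tables. The two parts disagree.

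**Step 3: size of one case.** Effect on the percentage = 100 × 1/n.

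- ALL EXT: 100 × 1/64 = 1.6 points. The 64 are enrolled subjects; the table uses those dosed, so 1.6 is a minimum.
- PBO-SEP, n = 32: 100 × 1/32 = 3.1 points.
- PBO-SEP, n = 21: 100 × 1/21 = 4.8 points.
- PBO-SEP, n = 16: 100 × 1/16 = 6.25 points.

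**The case against.** **The case may never arise.** No document says how many subjects entered with YMRS of 16 or more, the lead-in study's rules on mania are not available, and the investigator must judge each subject suitable. This stands. It limits the size of the point but not the gap in the definition.

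**A reader might infer that every PBO-SEP subject manic at entry is counted.** The text does not support that. The score must persist over two consecutive later visits or be high at the final one.

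**A reader might infer that the SAP breaks a convention it follows elsewhere.** The QTc criteria do require that the value be new, for example above "480 msec at any post-OL Baseline time point (including unscheduled visits) not present at OL Baseline". But the potentially-clinically-significant counts for laboratory values (SAP 18.2), other ECG values (18.3) and vital signs (18.4) explicitly disregard the baseline value. There is no uniform convention. The asymmetry that matters is between the two parts of the mania definition.

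**A reader might infer that Protocol 15.4.3.2 conceals the pre-existing episode by dropping the OL Baseline visit.** It does not. Dropping that visit stops a placebo-period score from serving as one of the two consecutive scores, which is partial protection. The OL Baseline score is still summarised and listed.

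**Over-counting is the cautious direction for safety, and a baseline gate could hide real events.** This is the strongest objection, and it defeats a flat requirement of OL Baseline below 16 for everyone. Such a gate would discard the new episode in row six. It would also remove SEP-SEP subjects whose mania began on SEP-4199 CR in the lead-in, whom Protocol 15.4.3.2 deliberately allows for. It does not defeat a rule limited to PBO-SEP that counts re-emergence and shows carried-over cases beside the main count.

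**Conclusion.** The YMRS part of SAP 18.6.2 can count, as emerging on SEP-4199 CR, a PBO-SEP episode that was already present at OL Baseline, when the score stays at 16 or more at two consecutive post-OL Baseline visits or is 16 or more at the final visit. The AE part would exclude the same episode. No other definition in the two documents closes the gap.

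Each such case is worth at least 1.6 points in ALL EXT, and 3.1 to 6.25 points in PBO-SEP if that group has 32 to 16 subjects. The group sizes are assumptions. The number of cases is unknown and may be zero. The point concerns how an endpoint is counted and labelled. It does not show that any reported incidence is wrong, and it is not a comment on who should have been enrolled.

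**What to change.** 1. In SAP 18.6.2, for PBO-SEP only, count the YMRS criterion as treatment-emergent if the OL Baseline total is below 16, or if the qualifying scores come after at least one post-OL Baseline score below 16.
2. In the same table, add a line for PBO-SEP subjects who meet the criterion only through an episode continuing from OL Baseline, labelled as YMRS of 16 or more already present at OL Baseline. Worsening of an existing episode then stays visible and no subject drops out of view.
3. Do not apply the condition to SEP-SEP, where onset may have been on SEP-4199 CR in the lead-in.
4. Leave the AE part unchanged.
5. Align the definitions in SAP 3.2.2, SAP 18.6.2, Protocol 11.4.6.2 and Protocol 15.4.3.2, which differ on one versus two visits, on use of the OL Baseline visit, and on what the final assessment is. Protocol 6.1 carries the same wording as SAP 3.2.2 and should follow.

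The cost is a short SAP insertion and one table line, from data already collected. The PBO-SEP incidence may come out slightly lower, with the difference shown beside it. If the database is already locked, the line can be added as a labelled supplementary row.

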6. STUDY ENDPOINTS

6.1. Safety Endpoints

- The incidence of overall AEs, discontinuation due to AEs, and SAEs
- The incidence of AESI including but not limited to hyperprolactinemia-related AEs
- Clinical laboratory evaluations (serum chemistry, hematology, thyroid panel, urinalysis)
- Clinical evaluation (vital signs including orthostatic effects, and 12-lead ECG measurements)
- Changes in prolactin values
- Changes in metabolic parameters (insulin, glucose, hemoglobin A1c (HbA1c), lipid panel)
- Change and percent change in body weight
- Change in body mass index (BMI)
- Incidence of treatment-emergent mania, defined as a YMRS total score ≥ 16 at post-Baseline visit (scheduled or unscheduled), or an adverse event of hypomania or mania
- Changes from Baseline in movement disorders scales: AIMS, BARS, and modified SAS
- Frequency and severity of suicidal ideation and suicidal behavior using the C-SSRS
- Change from Week 52/EOT (end of treatment) visit to the safety follow-up visit on the PWC

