11.4.6.2. Young Mania Rating Scale (YMRS)

The YMRS will be administered as a safety assessment and to inform the identification of treatment-emergent mania or hypomania.

The YMRS is a clinician-rated 11-item instrument used to assess the severity of mania in subjects with a diagnosis of bipolar disorder. The 11 items assess: Elevated Mood, Increased Motor Activity/Energy, Sexual Interest, Sleep, Irritability, Speech (Rate and Amount), Language/Thought Disorder, Content, Disruptive-Aggressive Behavior, Appearance, and Insight. The YMRS will be administered by a qualified rater at the site. Further information regarding administration of the YMRS, including rater training and qualification as well as recording of YMRS scores, will be provided in the Study Reference Manual.

Treatment-emergent mania or hypomania is defined as a YMRS total score \geq 16 at any 2 consecutive post-Baseline visits or at the final visit, or an AE of mania or hypomania.

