## 7.5. WINDOWING CONVENTIONS

No visit windowing will be performed during the analysis for this study. Data will be analyzed according

to the schedule outlined in the CSP. However, with the exception of SAE and PWC, any data collected beyond 7 days post the last OLE dose will be excluded from the efficacy and safety analyses unless otherwise specified; these data will be presented in data listings only.

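### The SAP does not define the final visit in treatment-emergent mania; read plainly, a first YMRS score of 16 or more at end of treatment can go uncounted, depending on the day of the follow-up visit

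*SAP*

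**What the plan says.** The documents define treatment-emergent mania in five places, in three forms.

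- **SAP 18.6.2**: YMRS total of 16 or more "at any 2 consecutive post-OL Baseline visits or at the final visit", or an adverse event (AE) of mania or hypomania. The post-OL Baseline period is described as "including both the OLE treatment period and the OLE follow-up period up to and including 7 days post the last OLE dose". YMRS is scheduled "from Visit 1E (coinciding with Visit 6 of SEP380-301) to Visit 15E".
- **Protocol 15.4.3.2** (the protocol's statistical definition): two consecutive OL visits, "or at the final assessment in the OL treatment period, or any treatment-emergent AE of mania or hypomania".
- **Protocol 11.4.6.2** (the assessment section): "at any 2 consecutive post-Baseline visits or at the final visit, or an AE of mania or hypomania". This is the same loose wording as the SAP.
- **Protocol 6.1 and SAP 3.2.2** (the endpoint lists): a score of 16 or more "at post-Baseline visit (scheduled or unscheduled), or an adverse event of hypomania or mania". One visit is enough.

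Four other provisions decide which visit is last:

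- Completers take their last dose on the morning of Visit 14E (Protocol 7.1).
- Visit 15E is 7 ± 2 days after the last dose and includes a YMRS (Protocol 11.6.15).
- SAP 7.5 says that "any data collected beyond 7 days post the last OLE dose will be excluded from the efficacy and safety analyses", unless otherwise specified. The named exceptions are SAEs and the PWC, not YMRS.
- The LOCF endpoint in SAP 7.3 stops at Visit 14E (EOT/ET), but SAP 18.6.2 does not use that boundary for mania.

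SAP 4.7, which lists changes from the protocol, does not mention the mania definition.

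**The concern.** The final-assessment condition catches a subject whose first high score comes at the last treatment-period visit, when no later treatment visit is left to confirm it. That includes the early termination visit. If the final visit is read as Visit 15E, this subject is tested on a score taken after dosing has stopped, and the end-of-treatment score no longer qualifies alone.

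The 7-day cut-off adds a second problem. It falls inside the permitted window for Visit 15E, so two subjects with identical scores can be classified differently because their follow-up appointments fell on different days. Two programmers could also read the undefined term differently and report different incidences. Treatment-emergent mania is a named safety endpoint in both documents.

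**Working it through.** No planned figure exists to reproduce; the check is a comparison of rules.

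**Inputs**

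- Visit 15E window: 7 − 2 = day 5 to 7 + 2 = day 9 after the last dose (Protocol 11.6.15).
- Data retained: up to and including day 7 (SAP 7.5, and the period stated in SAP 18.6.2).
- Enrolled: 64 (SAP 4.4).

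**Which visit is final on the plain reading of SAP 18.6.2**

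- Visit 15E on day 5, 6 or 7: retained, so Visit 15E is final.
- Visit 15E on day 8 or 9: excluded, so Visit 14E (EOT/ET) is final.

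Under Protocol 15.4.3.2 the condition refers to "at the final assessment in the OL treatment period", which does not depend on the day of Visit 15E.

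**All score patterns at the last three visits**

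1 means YMRS of 16 or more and 0 means below 16. All earlier scores are taken as below 16, with no mania or hypomania AE.

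| 13E, 14E, 15E | Protocol 15.4.3.2 | SAP 18.6.2, 15E on days 5–7 | SAP 18.6.2, 15E on days 8–9 |
|---|---|---|---|
| 0, 0, 0 | no | no | no |
| 0, 0, 1 | no | **yes** | no |
| 0, 1, 0 | yes | **no** | yes |
| 0, 1, 1 | yes | yes | yes |
| 1, 0, 0 | no | no | no |
| 1, 0, 1 | no | **yes** | no |
| 1, 1, 0 | yes | yes | yes |
| 1, 1, 1 | yes | yes | yes |

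With Visit 15E on days 5 to 7 the two rules disagree on 3 of 8 patterns; on days 8 and 9 they agree on all 8.

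- **(0, 1, 0)** is the missed case. It counts under Protocol 15.4.3.2 and under the single-visit endpoint in Protocol 6.1 and SAP 3.2.2, but not under SAP 18.6.2 when Visit 15E is on days 5 to 7.
- **(0, 1, 1)** is not missed, because Visits 14E and 15E form a consecutive pair. A Visit 15E score below 16 is therefore a necessary condition.
- **(0, 0, 1)** and **(1, 0, 1)** are post-treatment scores that the SAP would count and Protocol 15.4.3.2 would not.

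**Size per subject**

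1/64 = 0.0156, or about 1.6 percentage points, if all 64 enrolled subjects are in the Safety Population. Within PBO-SEP or SEP-SEP the step is larger, but the documents do not give those group sizes.

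**After the fix**

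With the condition tied to the last treatment-period YMRS, (0, 1, 0) counts and (0, 0, 1) and (1, 0, 1) do not, on every day from 5 to 9. All three disagreements disappear.

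**The case against.** **The SAP never says that Visit 15E is the final visit.** That is correct: the term is undefined. There is text for reading it as Visit 14E: the LOCF endpoint stops there (SAP 7.3), and SAP 4.7 drops follow-up summaries other than PWC. Against this, SAP 18.6.2 carries YMRS to Visit 15E and refers to follow-up to day 7. Even if that reference attaches only to the AE condition, nothing confines the final visit to the treatment period. Visit 15E remains the plain reading, not an express statement.

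**The SAP follows the protocol.** A reader might infer an undeclared departure from it. The documents do not support that without qualification, because Protocol 11.4.6.2 uses the same loose wording. The protocol is itself inconsistent; the SAP matches its assessment section and not its statistical section.

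**Counting scores to day 7 is the plan's convention.** A reader might infer that counting a Visit 15E score is an error in its own right. It is mostly convention: SAP 7.5 applies the window generally, and the treatment-emergent AE window in Protocol 15.4.3.1 also runs to 7 days. What stands is the missed end-of-treatment score and the dependence on the appointment date.

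**The case is narrow.** This also stands. A subject who leaves with a mood switch would often have an AE of mania or hypomania and be counted anyway. By-visit and LOCF summaries of YMRS would still show high scores in aggregate, and the listings keep every record.

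**The single-visit endpoint would absorb it.** If Protocol 6.1 and SAP 3.2.2 governed, the missed case would be counted and the final-visit condition would be redundant. But SAP 18.6.2 is the derivation the analysis will follow, and the SAP does not say which definition prevails.

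**Conclusion.** The point holds as a defect in the SAP wording: an undefined term whose plain reading conflicts with Protocol 15.4.3.2.

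A subject is affected by the missed-case problem only if all four conditions hold:

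1. the first YMRS of 16 or more is at end of treatment or early termination;
2. Visit 15E falls on days 5 to 7;
3. the Visit 15E score is below 16;
4. no mania or hypomania AE is recorded.

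Each such subject moves the overall incidence by about 1.6 percentage points, assuming that all 64 enrolled subjects were dosed and so belong to the Safety Population. The number of such subjects is unknown. Days 5 to 7 are three of the five permitted days, but a reader should not infer a 60% chance of misclassification: that is a count of calendar days, and the documents give no distribution of visit days or scores. Nor is every first high score at end of treatment lost, given conditions 2 to 4. The analysis is descriptive, so no test or error rate is affected; what changes is the reported incidence of a named safety endpoint.

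**What to change.** In SAP 18.6.2, replace the final-visit condition with: *or at the last non-missing YMRS assessment in the OLE treatment period (up to and including Visit 14E EOT/ET)*. This agrees with Protocol 15.4.3.2 and uses the boundary that SAP 7.3 already sets for LOCF. Because an early termination visit can take place after the last dose, state that the 7-day limit in SAP 7.3 and 7.4 applies to it here too.

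Reconcile the new sentence with Protocol 11.4.6.2 and with the single-visit endpoint in Protocol 6.1 and SAP 3.2.2, and say which definition governs the reported incidence. If the sponsor prefers to keep Visit 15E as the final visit, define it so and list the difference from Protocol 15.4.3.2 in SAP 4.7.

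Visit 15E scores of 16 or more can be identified in the listings. A separate summary line is optional, since SAP 4.7 drops follow-up summaries other than PWC.

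The cost is one sentence in the SAP, a short reconciling note and a small programming change. No new data are needed.
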